#### 2.4.1.3 Cumulative dose and average daily dose

Cumulative dose of a study treatment is defined as the total dose given during the study treatment exposure and will be summarized for each of the study treatment components.

The **planned cumulative dose** for a study treatment component refers to the total planned dose as per the protocol up to the last date of investigational drug administration.

The **actual cumulative dose** refers to the total actual dose administered, over the duration for which the patient is on the study treatment as documented in the Dose Administration eCRF.

For patients who did not take any drug the cumulative dose is by definition equal to zero.

For continuous dosing, the actual cumulative dose is the sum of the non-zero doses recorded over the dosing period and the planned cumulative dose is the planned starting dose summed over the same dosing period.

For intermittent dosing, the actual cumulative dose should be defined based on the days when the patient is assumed to have taken a non-zero dose during dosing periods.

Average daily dose is defined as Cumulative dose (mg) / Number of dosing days. Drug free day(s) are not counted as dosing days.

#### 2.4.1.4 Dose intensity and relative dose intensity

Dose intensity (DI) for patients with non-zero duration of exposure is defined as follows:

For ribociclib, DI is defined as

DI (mg/day) = Actual Cumulative dose (mg) / adjusted Duration of exposure (day).

For letrozole, DI is defined as

DI (mg/day) = Actual Cumulative dose (mg) / Duration of exposure (day).

For goserelin and leuprolide, DI is defined as

DI (mg/28 days) = Actual Cumulative dose (mg) / Duration of exposure (28 days).

For patients who did not take any drug the DI is by definition equal to zero.

Planned dose intensity (PDI) is the assigned dose by unit of time planned to be given to patients as per protocol in the same dose unit and unit of time as that of the Dose Intersity. The planned dose intersity for ribociclib is 600mg/day and the planned dose intersity for letrozole is 2.5mg/day. The planned dose intensity for goserelin is 3.6 mg/28 days. The

Novartis	Confidential	Page 24
SAP	22-Feb-2022 (1:27)	CLEE011A2404

planned dose intensity for leuprolide is 7.5 mg/28 days. Goserelin and leuprolide are admistered Day 1 of each cycle.

Relative dose intensity (RDI) is defined as follows for ribociclib and letrozole:

RDI = DI (mg/day) / PDI (mg/day).

For goserelin and leuprolide, RDI is defined as

RDI = DI (mg/28days) / PDI (mg/28days).

DI and RDI will be summarized separately for each of the study treatment components, but using the duration of exposure of each of the components. In particular, while calculating DI and RDI for ribociclib, the adjusted duration of exposure for ribociclib should be used instead of the duration of exposure for ribociclib. This takes account into the 'off' days when no ribociclib is expected to be administered.

#### 2.4.1.5 Dose reductions, interruptions or permanent discontinuations

The number of patients who have dose reductions, permanent discontinuations or interruptions, and the reasons, will be summarized separately for each of the study treatment components.

'Dose changed', 'Dose interrupted', and 'Dose permanently discontinued' fields from the Dosage Administration eCRF pages (DAR) will be used to determine the dose reductions, dose interruptions, and permanent discontinuations, respectively.

The corresponding fields 'Reason for dose change/dose interrupted' and 'Reason for permanent discontinuation' will be used to summarize the reasons.

A dose change is either 'change in prescribed dose level' or 'dosing error' where actual dose administered/total daily dose is different from the prescribed dose.

For the purpose of summarizing interruptions and reasons, in case multiple entries for interruption that are entered on consecutive days with different reasons will be counted as separate interruptions. However, if the reason is the same in this mentioned multiple entries on consecutive days, then it will be counted as one interruption.

Interruption: An interruption is defined as a 0mg dose given on one or more days during the period where a patient is not on the 'off' part of a treatment cycle, after which > 0 mg dose resumes. For patients who had dose interruption checked but never resumed non-zero dose, the dose interruption will not be counted. For example, in the sequence of 600 mg - 0 mg (dose break) - 0 mg (dose interruption) - 0 mg (dose permanently discontinuation) the 0 mg (dose interruption) will not be counted as a dose interruption.

**Reduction**: A dose change where the prescribed dose level is lower than the previous prescribed dose level or where the actual dose administered/total daily dose is lower than the calculated dose amount based on the prescribed dose. Therefore any dose change to correct a dosing error will not be considered a dose reduction. Due to dosing error if a patient took a dose during the dosing break with a dose that is lower than the previous dose, this will not be considered as dose reduction. For example, a patient took 600 mg from day 1-21, and on day

Novartis	Confidential	Page 25
SAP	22-Feb-2022 (1:27)	CLEE011A2404

22-28, the patient accidently took 200 mg per day which is supposed to be a dosing break. The patient resumed 600 mg dosing on day 29. This will not be considered as dosing reduction. Only dose change is collected in the eCRF, number of reductions will be derived programmatically based on the change and the direction of the change.

Missing data: If dose is recorded but regimen is missing or entered as 'none', it is assumed that the investigational drug was taken as per-protocol.

#### 2.4.2 **Prior**, concomitant and post therapies

#### 2.4.2.1 **Prior anti-cancer therapy**

The number and percentage of patients who received any prior anti-neoplastic medications, prior anti-neoplastic radiotherapy or prior anti-neoplastic surgery will be summarized. Prior anti-neoplastic medications will be summarized by therapy type (e.g. chemotherapy, hormonal therapy etc.), setting (e.g. adjuvant, metastatic, etc.) and also by lowest Anatomical Therapeutic Classification (ATC) class, preferred term. Summarises will include total number of regimens, best response, and time from last treatment to progression for the last therapy. For radiotherapy, time since last radiotherapy, locations and setting of last therapy will be summarized. For prior surgery, time since last surgery, procedure and residual disease of last therapy will be summarized.

Separate listings will be produced for prior anti-neoplastic medications, radiotherapy, and surgery.

Anti-neoplastic medications will be coded using the WHO Drug Dictionary (WHO-DD); anti-neoplastic surgery will be coded using MedDRA. Details regarding MedDRA and WHO-DD version will be included in the footnote in the tables/listings.

The above analyses will be performed using the FAS.

## 2.4.2.2 Post treatment anti-cancer therapy

Anti-neoplastic therapies since discontinuation of study treatment will be listed and summarized by ATC class, preferred term, overall and by treatment group by means of frequency counts and percentages using FAS.

## 2.4.2.3 Concomitant medications

Concomitant therapy is defined as all interventions (therapeutic treatments and procedures) other than the study treatment administered to a patient coinciding with the study treatment period. Concomitant therapy include medications (other than study drugs) starting on or after the start date of study treatment or medications starting prior to the start date of study treatment and continuing after the start date of study treatment.

Concomitant medications will be coded using the World Health Organization (WHO) Drug Reference Listing (DRL) dictionary that employs the WHO ATC classification system and summarized by lowest ATC class and preferred term using frequency counts and percentages. Surgical and medical procedures will be coded using MedDRA and summarized by SOC and preferred term. These summaries will include:

Novartis	Confidential	Page 26
SAP	22-Feb-2022 (1:27)	CLEE011A2404

- 1. Medications starting on or after the start of study treatment but no later than 30 days after start of last dose of study treatment and
- 2. Medications starting prior to start of study treatment and continuing after the start of study treatment.

All concomitant therapies will be listed. Any concomitant therapies starting and ending prior to the start of study treatment or starting more than 30 days after the last date of study treatment will be flagged in the listing. The safety set in Core Phase will be used for all concomitant medication tables and listings.

According to Study protocol, treatment with substances which are strong inhibitors, or inducers of CYP3A4/5, or substrates of CYP3A4/5 with a narrow therapeutic window, or medications with a known risk of QT prolongation should be avoided. These substances are listed (not comprehensive and is only meant to be used as a guide) in Table 2-3.

 Table 2-3
 List of prohibited medications during study drug treatment

Category	Drug Name
Strong CYP3A4/5 inhibitors	Boceprevir, clarithromycin, cobicistat, conivaptan, danoprevir/ritonavir, eltegravir/ritonavir, grapefruit juice, indinavir/ritonavir, itraconazole, ketoconazole, lopinavir/ritonavir, mibefradil, nefazodone, nelfinavir, posaconazole, ritonavir, saquinavir, saquinavir/ritonavir, telaprevir, telithromycin, tipranavir/ritonavir, troleandomycin, voriconazole
Strong CYP3A4/5 inducers	Avasimibe2,3, carbamazepine, mitotane, phenobarbital, phenytoin, rifabutin, rifampin (rifampicin)3, St. John's wort (hypericum perforatum)3
CYP3A4/5 substrates with NTI1	Alfentanil, apixaban (doses >2.5 mg only), aprepitant, astemizole, cisapride, cyclosporine, diergotamine, dihydroergotamine, ergotamine, fentanyl, lovastatin, nicardipine, nisoldipine, pimozide, quinidine, rivaroxaban, simvastatin, sirolimus, tacrolimus, terfenadine, thioridazine
Medications with a known risk for QT prolongation4	Amiodarone, anagrelide, arsenic trioxide, astemizole, azithromycin, bepridil, chloroquine, chlorpromazine, cilostazol, ciprofloxacin, cisapride, citalopram, clarithromycin, disopyramide, dofetilide, domperidone, donepezil, dronedarone, droperidol, erythromycin, escitalopram, flecainide, fluconazole, halofantrine, haloperidol, ibutilide, levofloxacin, levomethadyl, mesoridazine, methadone, moxifloxacin, ondansetron (i.v. only), pentamidine, pimozide, probucol, procainamide, propofol, quinidine, sevoflurane, sotalol, sparfloxacin, sulpiride, terfenadine, thioridazine, vandetanib, venlafaxine
Herbal preparations/ medications	Herbal preparations/medications are prohibited throughout the study. These herbal medications

Novartis	Confidential	Page 27
SAP	22-Feb-2022 (1:27)	CLEE011A2404

	include, but are not limited to: St. John's wort, Kava, ephedra (ma huang), gingko biloba, dehydroepiandrosterone (DHEA), yohimbe, saw palmetto, and ginseng. Patients should stop using these herbal medications 7 days prior to first dose of study drug.	
Other investigational and antineoplastic therapies	Other investigational therapies must not be used while the subject is on the study. Anticancer therapy (chemotherapy, biologic or radiation therapy, and surgery) other than the study treatments must not be given to subjects while the subject is on the study medication. If such agents are required for a subject then the subject must be discontinued study drug.	
 NTI = narrow therapeutic index drugs whose exposure-response indicates that increases in their exposure levels by the concerning of a context inhibitate may lead to conjugate opticate of a conjugate opticate opticate opticates and the conjugate opticates optica		

by the concomitant use of potent inhibitors may lead to serious safety concerns (e.g., Torsades de Pointes).  Herbal product

 P-gp inducer

 Source: www.qtdrugs.org (as of Apr 7, 2015)

However, some patients may take these substances during the treatment period and these concomitant medications will be selected via programming prior to database lock and tabulated and listed in the CSR using the appropriate analysis set (e.g. FAS). If there is an update for the list of prohibited medications (e.g. in protocol amendment), the most up-to-date list shall be used for the CSR.

Treatment with the prohibited substances mentioned above will be identified in the database as protocol deviations.

## 2.5 Analysis of the primary objective

The primary objective of this study is to further evaluate the safety and tolerability of ribociclib in combination with letrozole in men and postmenopausal women with HR+, HER2- aBC who received no prior hormonal therapy for advanced disease.

To evaluate the primary objective the number (%) of patients who experienced adverse events (AEs) will be calculated for the following AE categories:

- Any AEs
- Grade 3/4 AEs
- Serious Adverse Events (SAEs)
- AEs of Special Interest (Neutropenia (including febrile neutropenia), QT prolongation, hepatobiliary AEs)
- AEs leading to discontinuation
- AEs leading to dose reduction or dose interruption
- Deaths

Novartis	Confidential	Page 28
SAP	22-Feb-2022 (1:27)	CLEE011A2404

## 2.5.1 **Primary endpoint**

The primary endpoint of this study is the number (%) of patients who experienced adverse events (AEs):

- Any AEs
- Grade 3/4 AEs
- Serious Adverse Events (SAEs)
- AEs of Special Interest (Neutropenia including febrile neutropenia, QT prolongation, hepatobiliary AEs)
- AEs leading to discontinuation
- AEs leading to dose reduction or dose interruption
- Deaths

## 2.5.2 Statistical hypothesis, model, and method of analysis

No statistical hypotheses will be tested in this study. The primary endpoint (number (%) of AEs, Grade 3/4 AEs and SAEs, events of special interest, AEs leading discontinuation and deaths, and AEs leading dose reduction or dose interruption) will be summarized by count and percentage in Safety Set.

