10.4.2 Statistical hypothesis, model, and method of analysis

No statistical hypotheses will be tested in this study. The primary safety variable (AEs, Grade 3/4 AEs and SAEs, events of special interest, and AEs leading discontinuation and deaths) will be summarized by count and percentage in safety set.

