10.4.4 Supportive and Sensitivity analyses

Not applicable.

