10.8 Sample size calculation

A sample size of 3,000 patients is planned to be enrolled in this study to detect rare AEs (frequency ~0.1%) with high probability. This will allow for a greater precision when reporting rare, but clinically meaningful AEs (e.g. febrile neutropenia, QT prolongation, renal insufficiency, thromboembolic events, etc.). For example, if the rate of an AE is 0.1%, then the probability of observing at least 1 AEs out of 3000 patients is 95.0%. A sample size of 3,000 patients will allow for a meaningful safety analysis of specific patient subgroup of particular interest. For example, the expected size of male patients may be 30 (~ 0.1% of total population), patients with ECOG PS=2 may be 150 (~5% of total population), and patients with one prior line of chemotherapy may be 300 (~10% of total population). Table 10-1 below provides a 95% confidence interval (CI) and the corresponding width of the 95% CI, with different rates of rare AEs observed in [LEE011A2301] study) for overall population as well as for subgroups of various sizes.

Number of Patients	Number of AE	Rate	Lower 95% Cl	Upper 95% Cl	Width*
QT prolongatio	n (observed rate =	3.5%)			
30	1	0.0333	0.0008	0.1722	0.1713
150	5	0.0333	0.0109	0.0761	0.0652
300	10	0.0333	0.0161	0.0604	0.0443
3000	99	0.0330	0.0269	0.0400	0.0131
Febrile neutrop	enia (observed rat	e = 1.5%)			
30	0	0	0	0.1157	0.1157
150	3	0.020	0.0041	0.0573	0.0532
300	5	0.0167	0.0054	0.0385	0.0330
3000	45	0.0150	0.0110	0.0200	0.0091

Table 10-1 Confidence Intervals associated with AEs of interest for subgroups

Renal insufficiency / creatinine increase (observed rate = 0.5%)					
30	0	0	0	0.1157	0.1157
150	1	0.0067	0.0002	0.0366	0.0364
300	2	0.0067	0.0008	0.0239	0.0231
3000	15	0.0050	0.0028	0.0082	0.0054

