#### 2. on-treatment period:

Core Phase: For patients who discontinue after the Core Phase treatment, on-treatment period is defined as from date of first administration of study treatment to 30 days after date of last actual administration of any study treatment (including start and stop date). For patients who transition to the Extension Phase, on-treatment period is defined as from date of first administration of study treatment to the date of last actual administration of study treatment to the date of last actual administration of study treatment to the date of last actual administration of study treatment to the date of last actual administration of study treatment to the date of last actual administration of any study treatment in the Core Phase.

Extension Phase: from date after the first administration of study treatment in the Extension Phase to 30 days after date of last actual administration of any study treatment

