#### 2.2.6 Subgroup of interest

The following subgroups of interest may be used at interim and/or final analysis:

- Region (Latin American, Region Europe, Asia)
- Country (countries with at least 100 patients including, but not limited to US, Canada, Italy, Spain, France, Belgium, Czech Republic)
- Prior treatments for advanced disease (no treatments vs. chemotherapy)

Novartis	Confidential	Page 19
SAP	22-Feb-2022 (1:27)	CLEE011A2404

- Prior treatments for (neo)adjuvant (no treatments, endocrine only, chemotherapy only, both endocrine and chemotherapy )
- ECOG PS (PS 0-1 and 2)
- Liver involvement (yes vs. no)
- Lung involvement (yes vs. no)
- Lung or liver involvement (yes vs. no)
- Bone lesion only metastasis
- Other visceral/soft tissue involvement (adrenal, kidney, lymphonodes/soft tissue, etc.)
- Number of metastatic sites  $(0, 1, 2, \ge 3)$
- Age (<65, 65-<70, 70-<75, ≥75 years)
- Gender (male and female)
- Race (Asian vs. Non-Asian)
- Hormonal status at baseline (premenopausal vs. postmenopausal)

The objectives for carrying out analyses on these subgroups are to describe/characterize the treatment effect in these subgroups, to identify potential safety issues that may be limited to a subgroup of patients, or safety issues that are more commonly observed in a subgroup of patients.

With exception of male, summary tables will only be performed if at least 100 patients are present in each subgroup.

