#### 2.8.1 Adverse events

AE summaries will include all AEs occurring during on treatment period. All AEs collected in the AE eCRF page will be listed along with the information collected on those AEs e.g. AE relationship to study drug, AE outcome etc. AEs with start date outside of on-treatment period will be flagged in the listings.

AEs will be summarized by number and percentage of patients having at least one AE, having at least one AE in each primary system organ class (SOC) and for each preferred term (PT) using MedDRA coding. A patient with multiple occurrences of an AE will be counted only once in the respective AE category. A patient with multiple Common Terminology Criteria for Adverse Events (CTCAE) grades for the same preferred term will be summarized under the maximum CTCAE grade recorded for the event. AE with missing CTCAE grade will be included in the 'All grades' column of the summary tables.

In AE summaries, the primary system organ class will be presented alphabetically and the preferred terms will be sorted within primary SOC in descending frequency. The sort order for the preferred term will be based on their frequency.

Novartis	Confidential	Page 32
SAP	22-Feb-2022 (1:27)	CLEE011A2404

The following adverse event summaries will be produced; overview of adverse events and deaths, AEs by SOC and PT, summarized by relationship, seriousness, leading to treatment discontinuation, leading to dose interruption/adjustment, requiring additional therapy and leading to fatal outcome. In addition, a summary of serious adverse events with number of occurrences will be produced (an occurrence is defined as >1 day between start and prior end date of record of same preferred term).

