## Analysis of AESIs

An adverse event of special interest is a grouping of adverse events that are of scientific and medical concern specific to compound ribociclib. These groupings are defined using MedDRA terms, SMQs (standardized MedDRA queries), HGLTs (high level group terms), HLT (high level terms) and PTs (preferred terms). Customized SMQs (Novartis MedDRA queries, NMQ) may also be used. A NMQ is a customized group of search terms which defines a medical concept for which there is no official SMQ available or the available SMQ does not completely fit the need. It may include a combination of single terms and/or an existing SMQ, narrow or broad. For each specified AESI, number and percentage of patients with at least one event of the AESI occurring during on treatment period will be summarized.

Summaries of these AESIs will be provided, (specifying grade, SAE, relationship, leading to treatment discontinuation, leading to dose adjustment/interruption, hospitalization, death etc.). If sufficient number of events occurred, analysis of time to first occurrence will be applied.

A listing of all grouping levels down to the MedDRA preferred terms used to define each AESI will be generated.

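### Primary adverse-event results are bare percentages: no confidence intervals, and only a conditional, unspecified allowance for unequal time on treatment

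*SAP*

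**What the plan says.** **Primary analysis.** SAP 2.5.2 plans that the primary endpoint "will be summarized by count and percentage in Safety Set"; Protocol 10.4.2 has the same rule ("will be summarized by count and percentage in safety set"). Supportive analyses of this endpoint are marked as not applicable in SAP 2.5.4 and Protocol 10.4.4.

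**Counting.** SAP 2.8.1: "A patient with multiple occurrences of an AE will be counted only once in the respective AE category". In SAP 2.1.3 the Core Phase on-treatment window, for patients who do not enter the Extension Phase, runs "from date of first administration of study treatment to 30 days after date of last actual administration of any study treatment". For those who do, it ends at the last Core dose.

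**Precision and subgroups.** Protocol 10.8 first gives the chance of seeing at least one rare event (95.0% at a rate of 0.1%). It then points to Table 10-1, which "provides a 95% confidence interval (CI) and the corresponding width of the 95% CI" for 3,000 patients and for subgroups of 30, 150 and 300. SAP section 3 disclaims a statistical basis for the sample size but names precision for rare AEs as a benefit. SAP 2.2.6 wants subgroup analyses to reveal, among other things, "safety issues that are more commonly observed in a subgroup of patients". It requires at least 100 patients per subgroup, with men exempt.

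**Time on treatment.** For AESIs only, SAP 2.8.2 adds: "If sufficient number of events occurred, analysis of time to first occurrence will be applied". Duration of exposure is summarised in SAP 2.4.1, apart from the AE tables. ORR and CBR get exact binomial 95% intervals (SAP 2.7.2).

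**The concern.** Two things are missing from the tables that answer the primary objective.

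The first is precision. The protocol tells the reader how wide the intervals will be in groups of 30, 150 and 300, and the analysis then reports none. The lack of hypothesis tests does not explain this, since ORR and CBR are not tested either and still get intervals.

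The second is a way to compare subgroups whose treatment lasted for different times. A percentage over the on-treatment window combines how fast events occur with how long patients were exposed. The listed subgroups include ECOG 2, liver involvement and prior chemotherapy, where time on treatment could plausibly differ. If a subgroup stops early because of progression, events that would have come later are not counted. A table intended to reveal higher risk in that subgroup could then show lower risk. The only time-based analysis covers the AESIs, and SAP 2.8.2 gives no event threshold, method or subgroup use for it. It leaves out the other primary categories, as well as renal insufficiency and thromboembolic events, which Protocol 10.8 names as targets.

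**Working it through.** **1. The protocol's own figures.** Detection: 1 − 0.999^3000 = 0.9503 (stated 95.0%). Table 10-1: Clopper-Pearson limits are the 2.5% quantile of Beta(x, n−x+1) and the 97.5% quantile of Beta(x+1, n−x). All 12 intervals reproduce to four decimals. The QT rows are:

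| Events / n | Lower | Upper |
|---|---|---|
| 1/30 | 0.0008 | 0.1722 |
| 5/150 | 0.0109 | 0.0761 |
| 10/300 | 0.0161 | 0.0604 |
| 99/3000 | 0.0269 | 0.0400 |

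**2. What a bare percentage hides.** By the same method, 0/30 has an upper limit of 11.6%. At the 100-patient minimum, 0/100 has an upper limit of 3.6% and 3/100 runs from 0.6% to 8.5%.

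**3. Unequal exposure, constant hazard.** The documents give no exposure by subgroup, so these inputs are assumptions. With 18-month risk R, the crude percentage after t months is 1 − (1−R)^(t/18). For R = 10%:

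| Months treated | 6 | 9 | 12 | 18 |
|---|---|---|---|---|
| Crude % | 3.5 | 5.1 | 6.8 | 10.0 |

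The hazard is the same throughout: −ln(0.9)/18 × 1200 = 7.0 per 100 patient-years. For R from 3.5% to 60%, the 6-month value is 0.34 to 0.44 of the 18-month value. With exponential discontinuation (medians 6, 12 and 24 months, cap 24), the R = 10% event reads 4.6%, 7.2% and 9.5%.

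**4. Unequal exposure, the protocol's event timing.** Protocol 4.3 reports, from the earlier phase III study, QTc prolongation in the first 2 cycles, 83.8% of liver-test elevations in the first 6 cycles, and 85% of grade 3/4 neutropenia in the first 12 months. Full-follow-up risks are taken from Protocol 1.2.1.2.1: 3.3% (QTcF above 480 ms), 9.3% (grade 3/4 ALT) and 59.3% (grade 3/4 neutropenia). Assumptions: exponential time on treatment with median 8 or 20 months (μ = ln 2/median = 0.0866 or 0.0347), cap 26 months, independent of the AE; events spread evenly within each stated period, with any remainder spread to month 26.

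The share of events seen from a period (a, b) is (e^(−μa) − e^(−μb)) / (μ(b−a)).

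- QT, period 0 to 1.84 months (56 days): shares 0.924 and 0.969, so crude 3.05% and 3.20%.
- Liver tests, 0 to 5.52 months then to 26: 0.838 × 0.795 + 0.162 × 0.290 = 0.713, and 0.838 × 0.910 + 0.162 × 0.591 = 0.859; crude 6.6% and 8.0%.
- Neutropenia, 0 to 12 months then to 26: 0.85 × 0.622 + 0.15 × 0.205 = 0.559, and 0.85 × 0.818 + 0.15 × 0.523 = 0.774; crude 33.2% and 45.9%. The documents do not say how events fall within the first 12 months; if they cluster early, this gap shrinks.

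**5. Would patient-year rates repair this?** Mean time on treatment in the same model is (1 − e^(−26μ))/μ = 10.33 and 17.13 months. QT: 3.05/10.33 × 12 = 3.5 and 3.20/17.13 × 12 = 2.2 per 100 patient-years. Liver tests: 7.7 and 5.6. Underlying risk is identical, yet the short-exposure group looks about 58% worse on QT. The crude percentage was only about 5% too low.

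**The case against.** The strongest reply has four parts.

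- **Intervals can be derived.** They follow from the n and % already tabulated, and the study tests no hypotheses. This is true, so the omission is one of reporting and no information is lost. The cure is equally cheap, and few readers will compute intervals across many subgroup tables.
- **The sample size does not rest on interval width.** A reader might infer from Table 10-1 that it does. Protocol 10.8 puts detection probability first and SAP section 3 disclaims a statistical basis, so the table is only part of the justification. The point does not need more than that.
- **Time is not ignored.** Exposure is summarised, and AESIs may get a time-to-first-occurrence analysis. SAP 5.4 also has a general Kaplan-Meier paragraph that could be read as its method. However, that paragraph is not tied to AESIs and says nothing about how the end of treatment is handled.
- **The bias is not shown.** A reader might infer that shorter-treated subgroups will look safer, by a wide margin. The documents do not support that. They give no subgroup exposure times, and their own event timing makes the effect slight for QT. Where toxicity itself ends treatment, the subgroup with shorter treatment can show the higher percentage. Only the weaker statement stands: crude percentages can mislead for events that keep accruing.

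Subgroup analyses are also optional in SAP 2.2.6, and the 100-patient rule leaves men as the one very small group expected in the tables.

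**Conclusion.** The point stands in two parts of unequal strength.

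The absence of intervals is certain from the text. It is most visible for about 30 men, where 1 event gives an interval of 0.1% to 17.2%.

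The exposure issue is a conditional risk, and its size depends on assumptions the documents cannot settle. For median exposures of 8 and 20 months, the gap at identical underlying risk is about 0.15 points for QT, 1.4 for liver tests and up to about 13 for neutropenia if its events are spread evenly over the first year. These figures assume that stopping is unrelated to the AE, and none should be quoted as the trial's actual bias. Events per 100 patient-years might seem the natural remedy, but step 5 shows that they mislead in the other direction for front-loaded events.

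**What to change.** 1. In SAP 2.5.2 and 2.8, add Clopper-Pearson 95% intervals to the primary AE categories and the AESIs, overall and for every reported subgroup including men.
2. In SAP 2.8.2, make time to first occurrence unconditional for AESIs and for other key AEs compared across subgroups. Report cumulative incidence at fixed times, for example 6, 12 and 18 months.
3. State how the end of the on-treatment period is handled, because the options answer different questions. As a competing event, the result is the chance of the AE occurring on treatment by that time, which still depends on how long patients stay treated. As censoring, it is the risk had treatment continued, which requires stopping to be unrelated to the AE. State which one the subgroup comparison uses.
4. Do not rely on patient-year rates alone for early-onset events.

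The cost is extra table columns and a modest amount of programming. AE dates and dosing dates are already collected, so no new data are needed.
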